1 BACKGROUND

1.1 STUDY SYNOPSIS

Title	A Phase II Clinical Trial of PepCan Randomized and Double-Blinded to Two Therapy Arms for Treating Cervical High-Grade Squamous Intraepithelial Lesions
IRB Number	202790
Methodology	This is a Phase II study to evaluate the efficacy and safety of an HPV therapeutic vaccine called PepCan (HPV 16 E6 peptides combined with Candida skin testing reagent called Candin®) in adult females over a 12-month time period. As the results from the Phase I trial demonstrated some efficacy against non-16 HPV types, Candin® alone will also be tested. Therefore, there will be two treatment arms: (1) PepCan and (2) Candin®. Subjects found to be eligible for vaccination will be randomized in a double-blinded fashion at a 1:1 ratio. Each subject will be receiving injections four times with three weeks between injections. Clinical and virological responses will be assessed at 6- and 12-months. Safety will be assessed from the time of enrollment to 12-Month Visit. Immunological assessments will be made at 4 time points (prevaccination, after 2 injections, 6 months after 4 injections and 12 months after 4 vaccinations).
Study Duration	66 months
Study Center	University of Arkansas for Medical Sciences
Objectives	Primary Objective - To evaluate the efficacy of PepCan in humans Secondary Objectives - To evaluate the safety of PepCan in humans Tertiary Objective - To evaluate immunological response and viral clearance Other Outcome Measures - To identify factors predicting clinical and virological responses to PepCan; to evaluate vaccine effect; to examine mechanisms of cross-protection
Outcome Measures	Primary Outcome Measure: Clinical response as assessed by histological regression of HSIL at 12 months Secondary Outcome Measure: Safety Tertiary Outcome Measures: Immunological response and viral clearance Other Outcome Measures: Predicting vaccine response using various factors such as age, oral contraceptive use, smoking history, circulating immune cells, HLA types, HPV types, bacterial taxa, and cytokine/chemokine profiling; evaluating vaccine effect; determining cross-protection and examining epitope-spreading and cross-reactivity as possible mechanisms
Number of Subjects	125 adult women will be screened; up to 80 women will participate in the vaccination phase and will be randomized to PepCan and Candin® arms

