1.5.9 Rationale for Primary Outcome Measure: Efficacy

The clinical response to evaluate the vaccine efficacy will be assessed by comparing the punch biopsy results between the Screening Visit (having had HSIL to qualify for vaccination) and the 12-Month Visit (\pm 2 weeks) (Fig. 6). LEEP will not be performed to assess efficacy, but it will be offered at no cost to subjects who have persistent HSILs at the 12 Mo Visit.

The design of the proposed Phase II trial is single-site, and randomized to 2 treatment arms in a double-blinded fashion. We will use a historical placebo group from a clinical trial with similar design (i.e., enrollment of subjects with biopsy-proven CIN2/3, and clinical response assessed by biopsy in 15 month) for comparison [57]. The overall histological regression rate in the dose-escalation Phase I clinical trial was 52% three months after the last vaccination, and this is expected to substantially increase with an extended 12-month observation period.[18] Assuming a conservative rate of 60%, n=35 in the PepCan arm would give 91% power (two-tailed, $\alpha=0.05$) for detecting a statistically significant difference from the historical placebo group which had a 29% (34 of 117) regression rate [57]. Although there is greater uncertainty regarding the Candin®-only arm, there is $\geq 90\%$ power to detect a significant differences between the PepCan and Candin® arms under multiple plausible scenarios (for example, regression rates of 67% vs. 29%, or 85% vs. 50%). Forty subjects in each arm will be enrolled to ensure that at least 35 subjects in each would complete the study. While the use of historical placebo group is not as rigorous as having a concurrent placebo group, a concurrent placebo group with biopsy-proven CIN2/3 that would go untreated for 12 months would be difficult to ethically justify.

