1.5.11.2 Rationale for Measuring Circulating Immune Cells

The level of circulating immune cells, including Th1 cells, Th2 cells, regulatory T-cells (Treg), and myeloid-derived suppressor cells (MDSC), will be assessed before vaccination, after 2 vaccinations, 6 months after 4 vaccinations, and 12 months after 4 vaccinations. The data from the Phase I clinical trial indicated that PepCan may increase Th1 responses ($p=0.02$) and decrease Th2

responses resulting in increased effector immune activity (**Fig. 4**). Whether the levels of these circulating immune cells can be used to predict vaccine efficacy in terms of clinical response and viral clearance will be investigated. Vaccine effects on these factors will also be examined throughout the study (i.e., 6 and 12 months instead of 3 months).

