2.3 TERTIARY OBJECTIVES: IMMUNOLOGICAL RESPONSE & VIRAL CLEARANCE

Immunological assessment in terms of HPV-specific CD3 T-cell responses will be assessed using an IFN- γ ELISPOT assay while circulating levels of CD4, Th1, Th2, Treg, and MDSC cells will be assessed by FACS analysis before vaccination, after 2 vaccinations, 6 months after 4 vaccinations, and 12 months after 4 vaccinations. Virological assessments will be made at Screening, 6-Month, and 12-Month Visits.

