8.3.2 Measuring Immune Cells

8.3.2.1 Circulating Immune Cells ([name] Laboratory)

A small amount of PBMCs (approximately 3 x 10⁶ cells) from blood draws at Visit 1, Visit 3, and Visit 5 will also be used to monitor levels of circulating immune cells such as Tregs and MDSC to assess whether vaccination may decrease their levels [60]. Flow cytometry will be used to determine the number of CD4+ CD25+ FOXP3+ (Treg) [29] and CD11b+CD14+CD33+IL4R \square +HLA-DR \square neg (MDSC) cells [29, 61, 62]. T-bet (Th1), GATA3 (Th2), and/or ROR gammaT (TH17) positive cells may also be examined. The number of circulating immune cells will be determined before vaccination, after two, and after four injections.

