9.3.1.2 Circulating Immune Cells

The changes in percentage of circulating immune cells such as Th1, Th2, Treg, and MDSC will be compared after 2, 6 months after 4 vaccinations, and 12 months after 4 vaccinations with baseline as shown in Fig. 4. Paired t-test and one-way ANOVA will be performed to determine statistical significance separately for the PepCan and Candin® groups.

The differences between the percentages of each circulating immune cell types will be compared between the "responders" and the "non-responders" at pre-vaccination, post-2 vaccination, 6 months after post-4 vaccination, and 12 months after post-4 vaccination using Wilcoxon rank-sum test separately for the PepCan and Candin® groups.

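### The one-way ANOVA planned for repeated immune-cell measurements has no term for the woman, so as an overall test of change it is far too conservative

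*Protocol*

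**What the plan says.** Protocol Section 2.3 schedules the T-cell and immune-cell assessments "before vaccination, after 2 vaccinations, 6 months after 4 vaccinations, and 12 months after 4 vaccinations", and Section 1.5.11.2 repeats that schedule for Th1, Th2, Treg and MDSC. Each woman therefore supplies up to four values per cell type.

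Section 9.3.1.2 sets the comparison. Changes in cell percentages "will be compared after 2, 6 months after 4 vaccinations, and 12 months after 4 vaccinations with baseline as shown in Fig. 4", which makes three contrasts with baseline in each arm. The tests follow: "Paired t-test and one-way ANOVA will be performed to determine statistical significance separately for the PepCan and Candin® groups". No subject effect or repeated-measures form is attached to the ANOVA. Nothing says which of the two tests decides, or how the three contrasts are adjusted.

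The SAP covers baseline characteristics, efficacy and safety only, so it neither corrects nor clarifies this analysis. The synopsis (Section 1.1) ranks the endpoint third: "Tertiary Outcome Measures: Immunological response and viral clearance".

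**The concern.** One-way ANOVA assumes that the groups being compared are independent. Here the groups are time points, and the same women appear in all of them. Stable differences between women cancel out of any comparison over time, but the ordinary ANOVA leaves them in its error term. The F ratio is then too small, real changes are missed, and the stated 5% level is not the level at which the test operates.

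The protocol intends to follow vaccine effects on these cells out to 6 and 12 months. An overall test that rarely rejects, reported beside paired tests that do, leaves the reader without a rule for what was found.

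**Working it through.** The documents give no power, SD or correlation for the immune-cell analysis, so there is no planned figure to reproduce.

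**Inputs**
- Women per arm: n = 35 completers, from Section 1.5.9 ("Forty subjects in each arm will be enrolled to ensure that at least 35 subjects in each would complete the study").
- Time points: k = 4, from Sections 1.5.11.2, 2.3 and 9.3.1.2.
- Two-sided alpha of 0.05: stated in Section 1.5.9 for the primary endpoint only, and assumed here.
- Within-woman correlation rho: not given. Assumed range 0 to 0.7, equal for all pairs of times.
- Change: not given. Assumed shift d = 0.4 SD at all three post-baseline times, with 0.5 SD as a second case.

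**Step 1. Size of the ordinary one-way ANOVA.** With total variance 1 and no true change, the between-time mean square has expectation 1 − rho and the within-time mean square has expectation 1. The F ratio is therefore shrunk by about (1 − rho). The 5% critical value on 3 and 4 × 34 = 136 degrees of freedom is 2.67, so the size is approximately P(F > 2.67/(1 − rho)).
- rho 0.3: 2.67/0.7 = 3.82, size about 1.2%
- rho 0.5: 2.67/0.5 = 5.34, size about 0.2%

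Simulation with 40,000 runs gives 1.2% and 0.2%. At rho 0.7 the size is about 0.01% or less. At rho 0 it is 5%.

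**Step 2. Power of a repeated-measures ANOVA.** For means 0, d, d, d the sum of squares about their mean is 0.75d², which is 0.12 at d = 0.4. The noncentrality is 35 × 0.12/(1 − rho) = 4.2/(1 − rho), that is 4.2, 6.0, 8.4 and 14.0 for rho 0, 0.3, 0.5 and 0.7. Power comes from the noncentral F on 3 and 3 × 34 = 102 degrees of freedom.

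**Step 3. Power of one paired t-test.** The SD of a difference is √(2(1 − rho)), so the noncentrality is 0.4 × √35/√(2(1 − rho)): 1.67, 2.00, 2.37 and 3.06, on 34 degrees of freedom.

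**Results, shift 0.4 SD** (one-way ANOVA by simulation)

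| rho | One-way ANOVA | Repeated-measures ANOVA | One paired t-test, unadjusted |
|---|---|---|---|
| 0 | 36% | 36% | 37% |
| 0.3 | 29% | 50% | 49% |
| 0.5 | 22% | 66% | 63% |
| 0.7 | 15% | 88% | 84% |

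Relative to the repeated-measures test, the one-way ANOVA loses 0%, about 42%, 66% and 83% of the power. At 0.5 SD the powers at rho 0.3, 0.5 and 0.7 are 50%, 46% and 41% against 71%, 86% and 98%, a relative loss of about 29%, 46% and 58%.

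**Step 4. The three paired tests taken together.** They share the baseline value. With equal correlations, any two of the differences correlate at (1 − rho)/(2(1 − rho)) = 0.5, whatever rho is. In simulation, the chance that at least one of three unadjusted tests is falsely significant is about 12.6% per cell type per arm. Independent tests would give 1 − 0.95³ = 14.3%.

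**Step 5. Disagreement.** At 0.4 SD, at least one unadjusted paired test is significant while the one-way ANOVA is not in about 46%, 63% and 82% of simulated trials at rho 0.3, 0.5 and 0.7.

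**The case against.** The best reply is that the criticised sentence also plans a paired t-test. That is a suitable test for contrasts with baseline, and it is the test used for the upper panel of the Phase I figure that the section cites. A reader might infer from the ANOVA alone that the plan ignores the pairing and loses most of its power to see a vaccine effect. The documents do not support that. Each paired test has nearly the power of the repeated-measures ANOVA. With Bonferroni adjustment, the chance that at least one of the three is significant (56%, 71% and 91% at correlations 0.3, 0.5 and 0.7, shift 0.4 SD) is at least as high as for the repeated-measures test. This part of the reply stands.

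It does not rescue the ANOVA. Both tests are named as determining significance, no adjustment of the paired tests is planned, and no rule settles a disagreement between them.

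A second reply is that one-way ANOVA, written next to a paired test, may be shorthand for its repeated-measures form. The text does not say so and the SAP is silent. Followed as written, the test is the ordinary one. If the other was meant, saying so costs nothing.

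A third reply is that the assumptions drive the size of the loss. That is correct. Without correlation there is no loss, and at 0.5 SD with correlation 0.3 or 0.5 the loss is less than half.

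**Conclusion.** The point holds for the overall test only. As named, the one-way ANOVA does not fit repeated measurements on the same women. With n = 35 and positive correlation it runs well below its nominal 5% level (about 1.2% at correlation 0.3, 0.2% at 0.5). At a 0.4 SD shift it has 29% and 22% power where a repeated-measures ANOVA has 50% and 66%. The correlations, the shift and the equal-correlation pattern are assumptions. The direction of the error needs only positive within-woman correlation.

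The accompanying paired tests preserve the power for each contrast, but unadjusted they carry about 12.6% false positives across the three times. Of the two planned procedures, one is therefore too strict as an overall test and the other too lenient.

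The consequences are limited. This is a tertiary, within-arm analysis that does not enter the primary efficacy or safety comparisons, and the ANOVA's own error is conservative.

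**What to change.** In Section 9.3.1.2:
- Replace the one-way ANOVA with a repeated-measures ANOVA, or with a linear mixed model with a random woman effect and time as a factor, fitted within each arm. The visits are unevenly spaced, so also state how unequal correlations are handled, for example by a Greenhouse–Geisser correction or an unstructured covariance.
- Take the three contrasts with baseline from that model, with a stated adjustment such as Bonferroni or Holm.
- State that this overall test decides significance.

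The time points should be reconciled in the same edit. Section 8.3.2.1 lists three ("The number of circulating immune cells will be determined before vaccination, after two, and after four injections"), whereas Sections 1.5.11.2, 2.3 and 9.3.1.2 list four, running to 12 months.

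The cost is a few sentences in the protocol, or a short added section in the SAP. No new data, visits or assays are needed.

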9.3.2 Viral Clearance and Microbial Community

HPV-DNA and bacterial testing will be performed using Thin-Prep samples from Screening, 6-Month, and 12-Month Visits.

A correlation between clinical response and virological response (at least one HPV type becoming undetectable after vaccination) will be examined by drawing a contingency table for responder vs. non-responders and HPV persistence vs. HPV clearance separately for the PepCan and Candin® groups. Fisher's exact test will be used. The presence and abundance of microbial taxa from species to phylum level will be correlated with clinical response and other immunological parameters.

9.4 FACTORS CONTRIBUTING TO STUDY RECRUITMENT AND RETENTION

Based on data provided in "Screening Visit Questionnaire", "Early Termination Questionnaire", and "12-Month Visit Questionnaire", factors that contribute to subject recruitment and retention may be assessed. The Fisher's exact test will be used to compare factors such as frequent use of Facebook private group, motivation for entering the study, or having young children will be compared between the subjects who are withdrawn from the study early and the subjects who completed the study.

9.5 FACTORS PREDICTING CLINICAL RESPONSE AND VIRAL CLEARANCE

Variables for prediction of vaccine response will be analyzed, first by univariate analyses, and then multivariable analysis with variable selection using lasso[63] with ten-fold cross validation. Computations will be performed in the R and R/Bioconductor[64] environments. Variable selection using lasso will be implemented with the package glmmLasso, while enrichment analysis for Gene Ontology terms will be performed using topGO.

10 DATA AND SAFETY MONITORING PLAN

The PI will have the overall responsibility for assuring safety and gathering the data for with assistance from the co-investigators, sub-investigators, and research staff, under the guidance of the Institutional Review Board (IRB). As the sponsor, UAMS is responsible for providing quality monitoring for this study.

Clinical site monitoring will be conducted by the UAMS Office of Research Regulatory Affairs (ORRA) to ensure that the rights and well-being of human subjects are protected; the trial data are accurate, complete and verifiable from source documents; and the trial is conducted in compliance with currently approved protocol/amendment(s), ICH GCP, and applicable regulatory requirements.

Monitoring specialists from ORRA will conduct periodic on-site, comprehensive monitoring as determined by a protocol-specific monitoring plan, which will be provided by the ORRA Monitoring Unit.

10.1 DEFINITIONS

10.1.1 Adverse Event

An adverse event is any occurrence or worsening of an undesirable or unintended sign, symptom, or disease that is temporally associated with the use of the vaccine, and it will be graded according to the Common Terminology Criteria for Adverse Events (CTCAE) Version 4.03. Local and/or systemic adverse events may include itching, burning, pain, peeling, rash, oozing, redness, tenderness, scarring, fever, nausea, dizziness, and wheezing. The subjects will be allowed to use and provided analgesics (such as ibuprofen or naproxen) according to the appropriate dosages after injections to limit any adverse events that may occur. Any adverse event will be reviewed and considered related or not related to the vaccine. All applicable events will be reported to the IRB according to IRB policy 10.2 and the FDA according to 21 CFR 312.32.

10.1.2 Serious Adverse Event

A serious adverse event is any medical event that:

- Results in death
- Is an immediate threat to life
- Requires hospitalization or prolongation of existing hospitalization
- Is a congenital anomaly or birth defect, or
- Other important medical events that have not resulted in death, are not life-threatening, or do not require hospitalization, may be considered serious adverse events when, based upon the appropriate medical judgment, they are considered to jeopardize the subject and may require medical or surgical intervention to prevent one of the outcomes listed above.

10.2 ADVERSE EVENTS MONITORING

10.2.1 Time Period

Adverse events will be collected from the time of enrollment until the 12-Month Visit.

10.2.2 Collecting Procedure

Adverse events may be uncovered through any of these methods:

- Observing the subject
- Asking the subject to keep “Subject Diary”
- Receiving an unsolicited complaint from the subject

All adverse events will be recorded in either CRF and/or Communication Note as appropriate. In addition, all adverse events will be recorded in AERS.

10.2.3 Relationship to the Investigational Drug

The relationship between the adverse event and the investigational drug should be assessed using the following categories:

- **Definitely Related:** A direct cause and effect relationship between the investigational drug and the adverse event exists.
- **Possibly Related:** A direct cause and effect relationship between the investigational drug and the adverse event has not been clearly demonstrated, but is likely or very likely.
- **Unlikely Related:** A direct cause and effect relationship between the investigational drug and the adverse event is improbable, but not impossible.
- **Unrelated:** The adverse event is definitely not associated with the investigational drug.

10.3 REPORTING ADVERSE EVENTS

10.3.1 Standard Reporting

A summary of adverse events will be included in the annual IRB status report and the IND report to the FDA.

10.3.2 Expedited Reporting

A serious, unexpected (previously not expected in nature, severity, or degree of incidence), and drug-related adverse event is required to be reported to:

- The UAMS Research Support Center-Regulatory Affairs within 24 hours of PI being notified
- The FDA will be notified using the MedWatch Form 3500A within 10 days of PI being notified (<http://www.fda.gov/medwatch/safety/FDA-500A Fillable.pdf>)
- The UAMS IRB will be notified of events requiring expedited reporting within 10 days of PI being notified (see below if SAE is death)
- A drug-related death occurring while a subject is on the study must be reported to:
 - The UAMS IRB immediately
 - The FDA within 7 days of the investigator learning of the event
 - The cause of death and the investigator’s discussion regarding whether or not the death was drug-related should be described in a written report.

11 PROTOCOL DEVIATION AND PROTOCOL VIOLATION

11.1 DEFINITIONS

11.1.1 Protocol Deviation

A study event that is not covered under the existing protocol and represents a failure to comply with the protocol. Most deviations are minor and involuntary. If the deviations represent a variation from the approved protocol that could affect the safety and welfare of the subject, it must be reported to the UAMS IRB immediately.

Missing subject diaries will not be considered protocol deviations, as there are mechanisms in place to collect this information.

11.1.2 Protocol Violation

An event clearly occurring outside of the approved research activity, which also represents a failure to comply with the protocol, e.g., enrollment of a subject that fails to meet inclusion or exclusion criteria. A protocol violation refers to more serious non-compliance, which more often leads to exclusion of subjects from eligibility analysis or their discontinuation from the study.

11.2 REPORTING PROTOCOL DEVIATIONS AND PROTOCOL VIOLATIONS

11.2.1 Standard Reporting

If the protocol deviation/protocol violation does not represent a significant alteration in the approved protocol and/or affect the safety or welfare of the subject, it will be reported to the UAMS IRB at the time of Continuing Review.

11.2.2 Expedited Reporting

If the protocol deviation or protocol violation represents a significant alteration in the approved protocol and/or if it affects the safety or welfare of the subject, it must be reported to the UAMS IRB immediately.

12 ETHICAL CONSIDERATIONS AND REGULATORY COMPLIANCE

12.1 HUMAN SUBJECT PROTECTION

This study will be conducted in compliance with the protocol and with all applicable regulatory requirements.

12.2 UAMS IRB AND PROTOCOL REVIEW AND MONITORING COMMITTEE (PRMC)

- A copy of the protocol and informed consent documents will be approved by the UAMS IRB and PRMC prior to initiation of the study.
- The investigator must submit and obtain approval for any changes in the protocol or informed consent forms. The UAMS Research Support Center must also be notified and provided the revised documents.
- Annual status report will be submitted.
- Change of PI will be notified within 30 days.
- PI will sign a statement regarding the protection of human subjects and vulnerable population in CLARA.

12.3 INFORMED CONSENT

- Before a subject's participation in the trial, the investigator is responsible for obtaining written informed consent from the subject or the subject's legally acceptable representative.
- Before signing the consent, the subject must have received adequate explanation of the objectives, methods, anticipated benefits, and potential risks associated with the study, including age-specific standard of care guidelines as periodically released by the American Society of Colposcopy and Cervical Pathology.
- No study-related procedures are to be performed before the subject has given his/her written informed consent.
- The consent process must be recorded in the Informed Consent Process Note.
- A copy of the signed, written informed consent will be given to the subject.
- Original consent documents will be kept with the study record.

